2.3 Benefit/Risk Assessment

This natural history study may benefit patients with ALSP and carriers of the *CSF1R* mutation by facilitating the understanding and evaluation of the current standard-of-care practice and identifying ways to improve patient care. The subjects who participate in this study will receive no direct benefit other than thorough medical assessments, which will provide detailed information on their disease status. The risks of participation in the study are primarily those associated with collection of blood samples for biomarker analyses and lumbar puncture for subjects who participate in the optional CSF Biomarker Sub-study.

3 OBJECTIVES AND ENDPOINTS

3.1 Study Objectives

The objectives of the study are:

- To understand the phenotypic heterogeneity and phenotype/genotype correlation and natural history of ALSP.
- To develop and evaluate biomarkers for assessing disease progression in patients with ALSP.
- To create the foundation for a future synthetic control arm and provide run-in data for patients who qualify for interventional studies.

3.2 Study Endpoints

3.2.1 *Pharmacodynamic (Biomarker) Endpoints*

- Change from Baseline to Months 6, 12, 24, and 36 in NfL in blood
- Change from Baseline to Months 12, 24, and 36 in NfL, cytokine(s), soluble TREM2, and soluble CSF1R in CSF in subjects who provide informed consent to participate in an optional CSF Biomarker Sub-study
- Change from Baseline to Months 6, 12, 18, 24, 30, and 36 in structural and volumetric magnetic resonance imaging (MRI)

3.2.2 *Clinical Outcome Endpoints*

3.2.2.1 *Cognitive Assessments*

- Change from Baseline to Months 6, 12, 18, 24, 30, and 36 in the Montreal Cognitive Assessment (MoCA)
- Change from Baseline to Months 6, 12, 18, 24, 30, and 36 in the Clinical Dementia Rating Scale plus National Alzheimer's Coordinating Center-Frontotemporal Lobar Degeneration (CDR[®]+NACC-FTLD)
- Change from Baseline to Months 6, 12, 18, 24, 30, and 36 in the Brief Assessment of Cognition (BAC) battery

3.2.2.2 *Motor Assessments (Ambulatory Subjects)*

- Change from Baseline to Months 6, 12, 18, 24, 30, and 36 in the 2-Minute Walk Test (2MWT)
- Change from Baseline to Months 6, 12, 18, 24, 30, and 36 in the Timed Up and Go (TUG) test

3.2.2.3 Severity of Illness Assessments

- Clinical Global Impression – Change (CGI-C) responses at Months 6, 12, 18, 24, 30, and 36
- Patient Global Impression - Change (PGI-C) responses at Months 6, 12, 18, 24, 30, and 36

3.2.2.4 Other Functional and Psychiatric Assessments

- Change from Baseline to Months 6, 12, 18, 24, 30, and 36 in the Functional Activities Questionnaire (FAQ)
- Change from Baseline to Months 6, 12, 18, 24, 30, and 36 in the Neuropsychiatric Inventory – 12-Item Version (NPI-12)
- Change from Baseline to Months 6, 12, 18, 24, 30, and 36 in the Cortical Basal ganglia Functional Scale (CBFS)
- Change from Baseline to Months 6, 12, 18, 24, 30, and 36 in the Zarit Burden Interview

3.2.3 Safety Endpoints

- Adverse events (AEs)
- Columbia-Suicide Severity Rating Scale (C-SSRS)

4 STUDY DESIGN

4.1 Overall Design

This is a non-interventional, prospective, multicenter, observational, natural history study of patients with ALSP and asymptomatic carriers of *CSF1R* gene mutations, the causative mutation for ALSP. Potential study participants will be screened for study eligibility. Individuals who satisfy the study inclusion and exclusion criteria and who provide written informed consent will be enrolled in the study and followed for up to 36 months.

Clinic visits to assess disease status will be conducted at Screening/Baseline and at Months 6, 12, 18, 24, 30, and 36. Each clinic visit will include clinical assessments (cognitive, motor, functional, psychiatric, severity of illness, and study partner burden assessments) and imaging studies. Blood for biomarker analysis will be collected at Screening/Baseline and at Months 6, 12, 18, 24, 30, and 36. Adverse events (AEs) and concomitant medications and procedures will be recorded throughout the 36-month study.

An optional sub-study to evaluate levels of biomarkers in cerebrospinal fluid (CSF) is also included in this study and will be conducted at select study sites. A CSF sample will be obtained at Screening/Baseline and at Months 12, 24, and 36 from subjects who provide informed consent to participate in the optional CSF Biomarker Sub-study.

Given the nature of ALSP, subjects may progress while on study. If a subject is unable to attend on-site visits due to a decline in his/her condition and the subject is willing to remain in the study, telephone visits may be conducted at Month 18, Month 24, and Month 30 in lieu of clinic visits at the discretion of the Investigator (refer to schedule of assessments, [Table 1](#)) All other visits should occur in clinic. Telephone visits will also require participation of the study partner.

Subjects who, in the discretion of the investigator, may be eligible for a VGL101 clinical study may be discontinued from this study at any time. For subjects who discontinue from this study to enroll in a VGL101 clinical study, all procedures, except the MRI, blood biomarker sampling, and CSF collection (for subjects in the CSF Sub-study), will be collected once for the Early Termination (ET) Visit of this study and for the Screening or Baseline Visit of the VGL101 clinical study and will be analyzed as part of both studies. If CSF biomarker collection is not included at the Screening or Baseline Visit of the VGL101 clinical study, CSF biomarker collection will be performed at the ET Visit of this study.

4.2 Scientific Rationale for Study Design

4.2.1 *Study Design*

The open-label design is an appropriate design for a non-interventional study in which the natural course of the disease will be followed. The information that is collected in this study will be used to evaluate biomarkers for assessing disease progression in patients

with ALSP and, thereby, will contribute to the development of future novel therapies that focus on the neuropathophysiological features that underlie ALSP and that are essential to reverse, delay, or stop progression of this debilitating disorder.

4.2.2 *Pharmacodynamic (Biomarker) Endpoints*

Changes in NfL protein in blood (all subjects) and CSF (subjects who participate in the optional CSF Biomarker Sub-study) will be evaluated as potential neuropathophysiological biomarkers for ALSP. Studies have shown that NfL protein levels are markedly increased in the serum and CSF of patients with ALSP (Hayer et al, 2018), as well as in the blood and CSF of patients with other neurodegenerative diseases, including multiple sclerosis, amyotrophic lateral sclerosis (ALS), and frontal lobe dementia (Byrne et al, 2017; Niemelä et al, 2017; Merluzzi et al, 2019; Bäckström et al, 2020; Delaby et al, 2020). Thus, reduction in NfL levels may be predictive of clinical improvements and may serve as a surrogate endpoint in therapeutic studies of orphan neurodegenerative indications, including ALSP.

The response of microglial cells to changes in the environment of the central nervous system is activated through TREM2 and its associated protein kinase complex, DAP12 (Konishi & Kiyama, 2018). The TREM2/DAP12 signal functions as the primary regulator that transforms microglia from a homeostatic to a neural disease-associated state and produces an anti-inflammatory response and neurotrophic factors to protect injured neurons and enable nerve tissue regeneration. Animal and human genetic studies have demonstrated that microglia without TREM2 or with mutated TREM2 do not convert to an activated stage and, subsequently, lead to development and/or progression of neurologic disorders. Furthermore, animal models of Parkinson's disease, Alzheimer's disease, ALS, and demyelinating disease display dysregulation of TREM2/DAP12 signals that promotes pathogenesis of neurodegeneration (Konishi & Kiyama, 2018). TREM2 in CSF is a marker of CNS microglia activity. The utility of TREM2 as a target engagement biomarker warrants further evaluation; therefore, soluble TREM2 will be included as an exploratory biomarker in early clinical trials of VGL101.

CSF1R gene mutations are specific diagnostic features of patients with ALSP. As phosphatase and kinase proteins associated with the *CSF1R* gene regulate functions of macrophages, microglia, and neuronal pathways, disturbances of these proteins due to gene mutations, may also be implicated in the neuropathophysiology of ALSP (Rademakers et al, 2011; Lynch et al, 2016; Kraya et al, 2019). Additional research and case studies will likely confirm 1 or more of the above protein markers of neuronal, axonal, and glial cell damage and death as a meaningful surrogate endpoint for future novel therapies for ALSP. Thus, soluble CSF1R levels in CSF in an optional CSF Biomarker Sub-study. In addition to soluble CSF1R and soluble TREM2, measurement of cytokine levels will be included as an exploratory biomarker in CSF in an optional CSF Biomarker Sub-study. Cytokine assays may include, but are not limited to, the following: interferon gamma-inducible protein 10 (IP-10) and monocyte chemoattractant protein-1 (MCP-1), which have been proposed to serve as additional markers of CNS immune dysregulation.

Magnetic resonance imaging of the brains of patients with ALSP reveals high signaling of white matter disfigurement with darkened fat (T2-weighted) and fluid-attenuated inversion recovery (FLAIR) (Van Gerpen et al, 2008; Sundal et al, 2012; Bender et al, 2014; Konno et al, 2014; Konno et al, 2017a; Konno et al, 2017b). The high signaling is generally confined to the bifrontal or bifrontal parietal regions of the brain in the deep, subcortical, and periventricular areas, as well as in the corpus callosum and corticospinal tracts. Early onset white matter lesions are scattered and localized but develop confluence with progression of the disorder. Images also confirm enlarged ventricles consistent with white matter lesions and cerebral atrophy. Although atypical, MRI with diffusion-weighted imaging (DWI) has shown high signaling in the bipyramidal tracts that connect brain to spinal cord in a patient with ALSP (Li et al, 2020). Magnetic resonance imaging scans will be obtained throughout the study to monitor disease progression.

4.2.3 *Clinical Outcome Assessments*

The structural, genetic, and neuropathophysiological abnormalities of ALSP lead to the onset of neurologic symptoms, such as moderate to severe motor and neuropsychiatric impairments (Sundal & Wszolek, 2017; Konno et al, 2018; Oosterhoff et al, 2018; Tian et al, 2019; Kempthorne et al, 2020; Zhan et al, 2020; Zhou et al, 2020). The battery of cognitive, motor, and psychiatric scales that will be used in this study have been selected to assess the effects of ALSP on the core symptoms of the disease over time.

4.3 *Definition of End of Study*

The end of the study is defined as the last date on which the last subject completes the Month 36/ET Visit.

5 STUDY POPULATION

5.1 Inclusion Criteria

Subjects who meet all of the following criteria are eligible for the study:

General and Administrative

1. Male or female subjects aged ≥ 18 years on the day the informed consent form (ICF) is signed.
2. Subjects who are able, in the opinion of the investigator, to understand the nature of the study and to comply with the protocol requirements, including scheduled visits, blood sampling, and other study procedures, or who have a study partner or legal guardian who can understand and assist the subject in complying with the protocol requirements.
3. Subjects who are willing and able to refrain from use of any prohibited medication/treatments that are not permitted by the protocol throughout the study period.
4. Subjects who receive approval of sponsor medical personnel as to final suitability for the study.

Inclusion Criteria – Subjects with “Definitive ALSP”

5. Subjects who have documentation of a gene mutation in the *CSF1R* gene (prior to enrollment).
6. Subjects who fulfill both of the following criteria (a and b):
 - a. More than two findings of clinical signs or symptoms in any of the following categories:
 - i. Cognitive impairment or psychiatric problem
 - ii. Pyramidal signs on neurological examination
 - iii. Extrapyramidal signs, such as rigidity, tremor, abnormal gait, or bradykinesia
 - iv. Epilepsy
 - b. MRI findings consistent with ALSP: specifically, bilateral cerebral white matter lesions with or without thinning of the corpus callosum ([Konno et al, 2018; Appendix 3, Section 10.3](#)).

NOTE: Subjects with other causes of leukoencephalopathy, including vascular dementia, multiple sclerosis, or leukodystrophy (e.g., adrenoleukodystrophy, Krabbe disease, metachromatic leukodystrophy), will be excluded.

7. Subjects who, in the investigator’s opinion, have demonstrated clinical progression of their ALSP within the past year.
8. Subjects who have a score of ≥ 12 on the MoCA.
9. Subjects who are ambulatory with or without aids (cane, crutches, etc.) or, if restricted to a wheelchair, are still able to wheel self, transfer in and out of wheelchair, and walk up to 5 meters with or without aid.

NOTE: Subjects that are non-ambulatory for reasons other than progression of ALSP may be enrolled.

10. Subjects who meet the criteria for definitive ALSP must have a designated study partner (i.e. caregiver) who spends at least 4 hours per week with them. The study partner must be able and willing to assist the subject in complying with the study requirements, be able to provide information during study visits, and be willing to sign a study partner ICF. Subjects who do not have a study partner may be enrolled at the investigator's discretion if they are able to comply with protocol requirements.

Inclusion Criterion – Subjects with “Prodromal ALSP”

11. Subjects who have documentation of a gene mutation in *CSF1R* gene (prior to enrollment).
12. MRI findings consistent with ALSP: specifically, bilateral cerebral white matter lesions with or without thinning of the corpus callosum (Konno et al, 2018; [Appendix 3, Section 10.3](#)). Prodromal subjects may have none or up to and including 2 ALSP-related clinical signs or symptoms (i.e., they do not meet the clinical criteria outlined in 6a as “more than two”).
13. Subjects who meet the criteria for prodromal ALSP and who, at later study visits, meet the criteria for definitive ALSP should have a designated study partner for subsequent study visits who spends at least 4 hours per week with them unless otherwise approved by the sponsor and/or medical monitor. The study partner must be able and willing to assist the subject in complying with the study requirements, be able to provide information during study visits, and be willing to sign a study partner ICF. Subjects who do not have a study partner may continue the study at the investigator's discretion if they are able to comply with protocol requirements.

Informed Consent

14. Subjects who are capable of providing written informed consent, including signing and dating the ICF, or who have a study partner/legal guardian who can provide written informed consent (with subject assent).

Screening Assessments

15. Woman of childbearing potential must have a negative urine pregnancy test at Screening/Baseline.

5.2 Exclusion Criteria

Subjects will be excluded from the study for any of the following reasons:

Medical Conditions

1. Subjects with any neurological or psychiatric diseases that can produce cognitive, motor, or behavioral impairment similar to ALSP, including, but not limited to, Alzheimer's disease, frontotemporal dementia, ALS, stroke, Huntington disease, multiple sclerosis, Parkinson's disease, and Down syndrome, or with active alcohol/drug abuse.
2. Subjects with any concurrent diagnosis that may confound neuropsychological testing (e.g., hearing impairment, visual impairment).

3. Subjects with any concurrent diagnosis that may confound ambulation measurements (e.g., amputee).
4. Subjects with contraindications for undergoing a lumbar puncture, such as bleeding disorders, increased intracranial pressure, or abnormal spinal anatomy.
NOTE: Only for subjects who participate in the optional CSF Biomarker Sub-study.
5. Subjects who are unable to undergo MRI (e.g., implants not compatible for MRI, claustrophobia, inability to remain still that will prevent acquisition of a good quality scan).
6. Female subjects who are pregnant, planning pregnancy in the next 12 months, or breastfeeding.
7. Subjects who are at significant risk of suicidal or violent behavior, in the opinion of the investigator. If a subject answers “yes” to the Question 4 or 5 on the C-SSRS, a risk assessment should be done by a qualified healthcare professional to assess whether it is safe for the subject to participate in the study.
8. Subjects with a current history of major medical illness, such as renal failure, congestive heart failure, or advanced pulmonary disease, that could put the subject at additional risk if participating in the study.
9. Subjects with a history of cancer that required active treatment in the last 5 years, with the exception of in situ cervical cancer and basal cell carcinoma of the skin.
10. Subjects with any condition or situation that, in the opinion of the investigator or sponsor medical personnel, may place the subject at significant risk, confound the study results, or interfere significantly with the subject's participation in the study.
11. Subjects who have previously undergone HSCT or plan to undergo HSCT within 12 months of the Screening/Baseline visit.

Prior/Current Clinical Study Experience

12. Subjects who are concurrently enrolled in an investigational drug or device study or who received an investigational product within 30 days or 5 half-lives before signing the ICF.

Note: Subjects who are receiving VGL101 in a clinical study may enroll after conclusion of their participation in the VGL101 clinical study.

Other Exclusion Criteria

13. Subjects who are involved, directly or indirectly, in the conduct or administration of this study as an investigator, sub-investigator, study coordinator, or other study staff member.

5.3 Lifestyle Considerations

No lifestyle restrictions will be imposed.

5.4 Screen Failures

Screen failures are defined as subjects who consent to participate in the clinical study but are not subsequently enrolled. A minimal set of screen failure information is required to

ensure transparent reporting of screen failures to meet the Consolidated Standards of Reporting Trials (CONSORT) publishing requirements and to respond to queries from regulatory authorities. Minimal information includes demography, screen failure details, eligibility criteria, and any serious adverse event (SAE). If additional study procedures were performed during screening, information from these procedures should be recorded in the electronic case report form (eCRF).

Individuals who do not meet the criteria for participation in this study (screen failure) may be rescreened after discussion with the medical monitor and resolution of the issue that led to initial screen failure.

6 INVESTIGATIONAL MEDICINAL PRODUCT(S) AND CONCOMITANT THERAPY

6.1 Investigational Medicinal Product

No intervention will be administered. Subjects will receive their usual treatments for ASLP, as prescribed by their physicians.

6.2 Concomitant Therapy

All prescription and over-the-counter medications that have been taken during the 30 days before Screening/Baseline through the last study visit will be recorded in the eCRFs, along with the following: reason for use, dates of administration (including start and stop dates), dose, and frequency of administration. A complete history of medications for the treatment of ALSP will be recorded.

7 SUBJECT DISCONTINUATION/WITHDRAWAL

7.1 Subject Discontinuation/Withdrawal from the Study

Subjects may withdraw from the study at any time or may be withdrawn at any time, at the discretion of the investigator, for safety, behavioral, or compliance reasons. When a subject wishes to withdraw consent, it is important to distinguish between withdrawing his/her consent for a particular study procedure or visit versus withdrawing his/her consent from the study entirely (i.e., premature discontinuation). Reasons for premature discontinuation from the study include, but are not limited to, the following:

- Withdrawal of consent
- Death
- Intercurrent illness
- Unacceptable AEs
- Protocol violation or noncompliance
- Lost to follow-up
- Investigator discretion
- At request of the sponsor, regulatory agencies, or institutional review board/independent ethics committee (IRB/IEC)

An ET Visit (as shown for the Month 36 Visit in the Schedule of Assessments in [Table 1](#)) should be conducted at the time of study discontinuation.

For subjects who discontinue from this study to enroll in a VGL101 clinical study, blood biomarker collection will be performed once for both the ET Visit of this study and the Screening/Baseline Visit of the VGL101 study and will be analyzed as part of both studies.

For subjects who discontinue from this study to enroll in a VGL101 clinical study, an MRI will be collected once for both the ET Visit of this study and the Screening/Baseline Visit of the VGL101 clinical study and will be analyzed as part of both studies.

For subjects who participate in the CSF Sub-study and who discontinue from this study to enroll in a VGL101 clinical study, CSF biomarker collection will be performed at the Screening or Baseline Visit of the VGL101 clinical study and will be analyzed as part of both studies. If CSF collection is not included at the Screening or Baseline Visit of the VGL101 clinical study, CSF biomarker collection will be done at the ET Visit of this study.

If the subject withdraws consent for disclosure of future information, the sponsor may retain and continue to use any data that are collected before withdrawal of consent.

Subjects who withdraw from the study may request destruction of any samples that have been taken and not tested, and the investigator must document this in the site study records.

7.2 Lost to Follow-up

A subject will be considered lost to follow-up if he or she repeatedly fails to return for scheduled visits and is unable to be contacted by the investigative site. The site must attempt to contact the subject and reschedule the missed visit as soon as possible and must counsel the subject on the importance of maintaining the assigned visit schedule and ascertain whether or not the subject wishes to and/or should continue in the study.

Before a subject is deemed lost to follow up, the investigator or designee must make every effort to regain contact with the subject (where possible, 3 telephone calls). These contact attempts should be documented in the subject's medical record. Subjects who continue to be unreachable will be considered to have withdrawn from the study.

Attempts will be made to determine the survival status (alive or deceased) of any subjects who fail to return for their study visit or who discontinue from the study before completing the 24-month (subjects who withdraw from the study before implementation of Amendment 3) or 36-month (subjects who withdraw from the study after implementation of Amendment 3) observation period. Study staff will contact the subject or the subject's study partner by telephone to determine survival status 24 or 36 months, respectively, after the date of the subject's Screening Visit or at the end of the study, whichever occurs sooner.

Discontinuation of specific sites or of the study as a whole is described in Appendix 1 ([Section 10.1.6](#)).

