8.6 Survival Assessment

Attempts will be made to determine the survival status (alive or deceased) of any subject who fails to return for the vial visit or who discontinues from the study before completing the 24-month (subjects who withdraw from the study before implementation of Amendment 3) or 36-month (subjects who withdraw from the study after implementation of Amendment 3) observation period. Study staff will contact the subject or the subject's study partner by telephone to determine survival status 36 months after the date of the subject's Screening Visit or at the end of the study, whichever occurs sooner.

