### 3 Objectives and Endpoints

#### 3.1 Study Objectives

The Illuminate NHS objectives are as follows:

- To understand the phenotypic heterogeneity and phenotype/genotype correlation and natural history of ALSP.

- To develop and evaluate biomarkers for assessing disease progression in patients with ALSP.
- To create the foundation for a future external control arm and provide run-in data for patients who qualify for interventional studies.

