#### **4.5.4 Survival**

The number and percentage of subjects who have died will be summarized.

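### The death summary in SAP 4.5.4 does not separate outcomes before and after transfer to a VGL101 study, although survival status is sought in everyone who discontinues

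*Protocol*

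**What the plan says.** Protocol 7.2 provides for attempts to "determine the survival status (alive or deceased) of any subjects who fail to return for their study visit or who discontinue from the study" early. On discontinuation, the rule covers those "who discontinue from the study before completing the 24-month (subjects who withdraw from the study before implementation of Amendment 3) or 36-month" observation period. Study staff telephone the subject or study partner to learn "survival status 24 or 36 months, respectively, after the date of the" Screening Visit, "or at the end of the study, whichever occurs sooner". The 24-month limit applies to those who withdrew before Amendment 3 was implemented, and the 36-month limit to those who withdrew after it. The duty is repeated in Protocol 1.2 (Schema), 1.3 (Table 1, footnote i) and 8.6, and in SAP Section 2 (Figure 1 footnote), 6.1 (Table 3, footnote i) and 6.2.2.4.

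Leaving for the drug programme is one form of discontinuation. Under Protocol 4.1, subjects who in the investigator's judgement "may be eligible for a VGL101 clinical study may be discontinued from this study at any time". SAP Section 1 names early termination to join the Phase 2 study as an important consideration for the analysis. Protocol 7.1 sets out how blood, MRI and CSF are handled for these subjects. No corresponding rule covers survival.

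The whole survival analysis is one sentence in SAP 4.5.4: "The number and percentage of subjects who have died will be summarized". SAP 4.5 applies safety summaries to the Study Population and to the prodromal and symptomatic subgroups, the latter also split by prior HSCT. None is defined by transfer. SAP 3.3.1.2 defines the Study Population by consent and eligibility, and neither removes transferred subjects nor truncates their follow-up.

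One study objective, in SAP 3.1, is "To create the foundation for a future external control arm".

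**The concern.** A natural-history death figure should describe what happens without the investigational drug. Under the plan as written, a subject who transfers and dies after dosing is counted as a death if the contact finds it. A subject who transfers and is found alive stays in the denominator as a survivor.

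If the drug lowers mortality, the natural-history figure comes out too low. If it raises mortality, the figure comes out too high. In any later comparison that used the figure as an untreated control, both errors would shrink the apparent difference.

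The rest of this study's data would not show a reader what had happened. Adverse events are collected only up to the ET visit in subjects who leave early (Protocol 8.4.1). Concomitant medication is recorded only to the last study visit (Protocol 6.2). Apart from follow-up of events already open at exit, the survival contact is the planned route by which a death after transfer reaches this dataset, and it arrives with no exposure information attached.

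**Working it through.** **Reading the rules together.**
1. Survival contact: every early discontinuation, with no exception (Protocol 7.2).
2. Transfer to a VGL101 study: an early discontinuation (Protocol 4.1).
3. Analysis: number and percentage of deaths in the Study Population and subgroups, with no cut at transfer (SAP 4.5.4, 4.5, 3.3.1.2).

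It follows that outcomes after transfer are included. The plan contains no mortality figure to reproduce, and the sample size of about 60 rests on no power calculation (Protocol 9.1, SAP 4.1.4).

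**Illustration of size (assumptions, not document figures).** Protocol 2.2.1 gives a mean of 6-8 years from symptom onset to death. I take 7 years, apply it from study entry, and assume a constant hazard of 1/7 per year. Of 60 subjects, 12 transfer at Month 12, drawn from those then alive without regard to risk. The horizon is 36 months.

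- Untreated 36-month mortality: 1 − exp(−3/7) = 34.9%.
- Deaths in the first 12 months: 60 × (1 − exp(−1/7)) = 7.99, leaving 52.01 alive. After 12 transfer, 40.01 remain.
- Later deaths among those remaining: 40.01 × (1 − exp(−2/7)) = 9.94.
- Deaths after transfer: with hazard ratio 1, 12 × (1 − exp(−2/7)) = 2.98; with hazard ratio 0.5, 12 × (1 − exp(−1/7)) = 1.60.

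| Summary | Calculation | 36-month result |
|---|---|---|
| As planned, hazard ratio 1 | (7.99 + 9.94 + 2.98)/60 | 34.9% |
| As planned, hazard ratio 0.5 | (7.99 + 9.94 + 1.60)/60 | 32.5% |
| Pre-transfer deaths over all 60 | (7.99 + 9.94)/60 | 29.9% |
| Kaplan-Meier, censored at transfer | 1 − (52.01/60) × (1 − 9.94/40.01) | 34.9% |

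The person-year version agrees. Person-years before transfer are 7 × (7.99 + 9.94) = 125.5, and 17.93/125.5 = 0.143 per year, which is 1/7.

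Two things follow. The planned percentage is distorted only to the extent that the drug changes mortality. Dropping post-transfer deaths while keeping every subject in the denominator is worse than the plan in both scenarios, because it treats transferred subjects as if they could not die.

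**Range of deaths after transfer.** Let 10% to 40% of 60 transfer at Month 12, with mean survival of 6 to 8 years and a hazard ratio of 0.5 to 1. The lowest case is 6 × (1 − exp(−1/8)) = 0.7 deaths. The highest is 24 × (1 − exp(−2/6)) = 6.8 deaths.

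**Timing of the contact.** Protocol 8.6 has staff make contact "by telephone to determine survival status 36 months after the date of the" Screening Visit, and SAP 6.2.2.4 also gives 36 months only. Protocol 1.2, 1.3 and 7.2 and SAP Figure 1 and Table 3 give 24 or 36 months, according to when the subject withdrew. For someone who transferred before Amendment 3, the difference is up to 12 more months of post-transfer outcome.

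**The case against.** The strongest reply is that survival carries little weight here. It is not among the endpoints in Protocol 3.2, where the safety endpoints are adverse events and the C-SSRS. The repeated-measures models in SAP 4.3.4 concern ventricle volume, MoCA and CBFS. The integrated analysis involves the Phase 2 study, which has its own SAP that is not among these documents and may deal with transfer. The contact is only an attempt and may fall at study end. This SAP serves an interim analysis with a database freeze around 11 April 2025, when some contacts may not yet be due. All of this stands, and it limits the consequence. It does not supply the missing rule: this study's own death table would still mix the two periods.

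A reader might infer more than the documents support.

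- **That survival time on the drug is analysed as natural history.** No survival-time, Kaplan-Meier or person-time analysis is planned; the output is a count and a percentage.
- **That a definite share of follow-up is contaminated.** With k subjects moving at Month m and a 36-month horizon, k(36 − m)/(60 × 36) gives 5.6% (10 at Month 24), 12.5% (15 at Month 18) or 22.2% (20 at Month 12). On the 24-month horizon, k(24 − m)/(60 × 24) gives 0%, 6.25% and 16.7%. The numbers moving are assumed, deaths are ignored, and the SAP computes no such quantity.
- **That the same death is counted in both studies.** That depends on Phase 2 documents not available here.
- **That the plan declares post-transfer deaths to be natural history.** It does not. The result follows from silence in SAP 4.5.4.

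**Conclusion.** The point holds as a gap in the analysis rule. Carried out exactly as written, the plan puts outcomes after possible VGL101 exposure into the natural-history death summary, with nothing to identify them. The size cannot be determined, because the documents give neither the number of transfers nor a mortality rate for this cohort. The illustrations (32.5% against 34.9%, and 0.7 to 6.8 deaths after transfer) rest on an assumed transfer number and time, a constant hazard, assumed hazard ratios, and a mean survival from symptom onset applied from study entry. The table is descriptive and survival is not a listed endpoint, so no main result is at risk. The correction is still worth making because it is cheap and protects the external-control objective.

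**What to change.** In SAP 4.5.4:

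- Report deaths before and after transfer to a VGL101 study separately, with the number of subjects who transferred.
- Summarise natural-history survival with follow-up censored at the ET visit or at the first VGL101 dose, naming in advance which is used. Use a Kaplan-Meier estimate or deaths per person-year, not pre-transfer deaths as a percentage of all enrolled subjects.
- State the assumption that transfer is unrelated to the risk of death. It may be doubtful, since those who transfer must qualify for an interventional study.

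Keep the survival contact as planned. Record the date of entry to the VGL101 study and the date of death; the documents describe the contact as returning only alive or deceased.

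Reconcile the contact time between Protocol 8.6 and SAP 6.2.2.4 (36 months only) and Protocol 1.2, 1.3 and 7.2, SAP Figure 1 and SAP Table 3 (24 or 36 months).

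The cost is a few lines of SAP text and two dates. The price in the analysis is less follow-up time in the censored estimate, and reliance on the assumption above.
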